#### Exclusion Criteria

- ♣ Severe malaria with complication sign and symptoms (see Annex I)
- ♣ Signs or symptoms of severe malnutrition, defined as weight-for-age  $\leq$  3 standard deviations below the mean, symmetrical edema involving at least the feet, or mid-upper arm circumference <100 cm for children less than five years of age (NCHS/WHO normalized reference values; see Annex I)
- ♣ Mixed plasmodium infection
- ♣ Severe anemia, defined as hemoglobin (Hb) < 8 g/dl

- ♣ Presence of febrile conditions caused by diseases other than malaria (e.g. measles, acute lower respiratory tract infection, severe diarrhea with dehydration)
- ♣ Serious or chronic medical condition (e.g. cardiac, renal, hepatic diseases, sickle cell disease, HIV/AIDS)
- ♣ Positive pregnancy test or breastfeeding
- ♣ Unable or unwilling to take contraceptives for women of child-bearing age
- ♣ Children weighing less than 5 kilograms
- ♣ History of hypersensitivity reaction to any medication tested or used as an alternative treatment
- ♣ Participants with history of prolonged QT conditions
- ♣ Taking regular medication, which may interfere with antimalarial pharmacokinetics or efficacy (see Annex VII)?

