## Rescue Treatment

Patients failing in any arm will be treated with second line drug per National Guidelines. Whereas, patients failing with the second line will be administered as of severe malaria criteria that is an indication of treatment failure.

The following are the known efficacy and adverse effects and pharmacokinetics of treatment drugs that will be used in the study:

**Chloroquine Plus Primaquine (CQ+PQ):** Chloroquine Plus Primaquine is a WHO Pre-qualified anti-malarial and FDA approved; WHO certifies the quality, safety and efficacy of the medication, and verifies that the manufacturer complies with WHO Good Manufacturing Practices. CQ+PQ is currently the first line anti-malarial recommended by Ethiopia FMOH for the treatment of uncomplicated falciparum infection. Adverse events are generally mild, most commonly GI (vomiting and diarrhea) and hematologic (anemia and eosinophilia). Its safety will be demonstrated in studies from Ethiopia and Uganda. Chloroquine has a half-life of 30-60 hours (53,54), while primaquine has a elimination half-life of 5-7 hours (54).

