### **Safety Assessment**

Safety will be assessed by recording the nature and incidence of adverse events and serious adverse events. Adverse events will be assessed by direct questioning. An adverse event is defined as any unfavourable, unintended sign, symptom, syndrome or disease that develops or worsens with the use of a medicinal product, regardless of whether it is related to the medicinal product. All adverse events must be recorded on the case report form. A serious adverse event is defined as any untoward medical occurrence that at any dose:

- results in death, is life threatening
- requires hospitalization or prolongation of hospitalization
- results in a persistent or significant disability or incapacity
- Is a congenital anomaly or birth defect.

‘Life-threatening’ means that the person will be at immediate risk for death; it does not refer to an adverse event that might have caused death if it were more severe. ‘Persistent or significant disability or incapacity’ means that a person’s ability to carry out normal life functions is substantially disrupted. All serious adverse events occurring during the study must be recorded and reported by the principal investigator to the sponsor, regardless of whether the principal investigator considers the events to be related to the investigated medicine. The investigator will collect information on all people who become pregnant while participating in this study and will record the information on the appropriate form. The person will also be followed to determine the outcome of the pregnancy.

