## Statistical Analysis

Every data from recruited patients will be imported into the WHO Excel sheet (double entry) which is designed for analysis of therapeutic efficacy study data. Data will be also entered in to IBM SPSS (version-26) software to calculate descriptive statistics (mean, median, standard deviations, range). Independent sample t-test will be used to compare baseline temperature and parasitemia between children and adults; mean blood Hb level at D0, D14, D28 and D42 between patients with parasitemia  $\geq 10,000$  and  $< 10,000/\mu\text{l}$  blood. Non-parametric (median) test for independent sample will be used to compare D1 parasitemia between children and adults and paired sample t-test will be used to compare mean Hb level between D0 and D14, D0 and D28, D14 and D28, D0 and D42, D28 and D42. All comparisons will be performed at 95% CI and significance level of 0.05.

Kaplan Meier (K-M) survival analysis and per protocol (PP) analysis will be used for estimation of primary outcomes and PP analysis method will be used to analyze secondary outcomes. The K-M survival analysis method provides better approximation of cure rates as it incorporates probabilities for censored data (incomplete observations due to LFU and withdrawals) in to the analysis. The WHO excel sheet is especially designed for estimation of cure rate based on K-M survival estimator analysis method.

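### No within-patient summary of haemoglobin falls is planned and no rule says when a measured fall is an adverse event, so tests on mean Hb can show recovery while a few patients fall steeply

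*Combined protocol and SAP*

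**What the plan says.** **Hb analyses.** Hb is measured on days 0, 14, 28 and 42 (Laboratory Examination; Annex 9). The Statistical Analysis section names two sets of Hb comparisons:
- independent t-tests of "mean blood Hb level at D0, D14, D28 and D42 between patients with parasitemia" at or above versus below 10,000/µl;
- a "paired sample t-test will be used to compare mean Hb level between D0 and D14", and likewise for four further pairs of visits.

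For both, "All comparisons will be performed at 95% CI and significance level of 0.05". The section also plans "to calculate descriptive statistics (mean, median, standard deviations, range", without saying for which variables. It adds that "PP analysis method will be used to analyze secondary outcomes".

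**Adverse events.** The Rescue Treatment section lists the common adverse effects of the regimen, including "hematologic (anemia and eosinophilia". The Safety Assessment section states: "Adverse events will be assessed by direct questioning". The Safety endpoints section describes asking patients about symptoms at each visit. The adverse-event codes on the case record form comprise 13 items, none of them anaemia or a laboratory value, and a fourteenth for anything else.

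**Withdrawal.** Patients hospitalised for severe side-effects are withdrawn (Patient Discontinuation or Protocol Violation).

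**Hb limits.** The Exclusion Criteria give "Severe anemia, defined as hemoglobin (Hb) < 8 g/dl". The Enrollment and Follow-up section excludes below 5 g/dl. Emergency Care and the Annex 1 screening form also use 5 g/dl. Annex 6 uses 5 g/dl in children and 7 g/dl in adults, together with a parasite-count condition.

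**The concern.** The protocol expects a haematological effect and measures Hb four times in each patient, yet plans no result that shows the effect patient by patient. A mean mixes two processes: recovery from malaria in most patients, and a possible large fall in a few. The first can hide the second.

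The adverse-event route does not reliably close the gap. A patient whose Hb drops by several g/dl without complaint, and who stays above 5 g/dl, has no defined path into the adverse-event incidence. Someone may record the fall, but nothing requires it.

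At stake is what the trial can say on haematological safety. It could report that mean Hb recovered without being able to say how many patients lost a large amount of Hb.

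**Working it through.** **1. The plan's own sample size.** 1.96² × 0.05 × 0.95 / 0.05² = 72.99, rounded up to 73. Then 73 × 1.2 = 87.6, rounded up to 88. Both match the plan. The 73 is used below.

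**2. Assumed Hb inputs.** The documents give no Hb mean, change or SD. Assume an SD of within-patient change of 1.5 g/dl, k = 4 patients with an extra 4 g/dl fall, and a mean change G of 0, 0.5 or 1.0 g/dl in the other 69.

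**3. Approximate calculation of the day 0 to day 14 paired t-test.**
- Expected mean change = G − (4 × 4)/73 = G − 0.22, that is −0.22, +0.28 and +0.78.
- Expected SD of the 73 changes = √[1.5² + 4² × (4 × 69)/(73 × 72)] = √(2.25 + 0.84) = 1.76.
- With a critical t of 1.993 on 72 df, significance needs a mean change beyond ±1.993 × 1.76/√73 = ±0.41.
- With the number of fallers fixed, the sample mean varies with SE = 1.5/√73 = 0.176.
- G = 0: P(mean < −0.41) = Φ((−0.41 + 0.22)/0.176) = Φ(−1.09) ≈ 14%.
- G = 0.5: P(mean > 0.41) = 1 − Φ((0.41 − 0.28)/0.176) = 1 − Φ(0.74) ≈ 23%.
- G = 1.0: P(mean > 0.41) = 1 − Φ((0.41 − 0.78)/0.176) = 1 − Φ(−2.11) ≈ 98%.

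**4. Simulation under the same assumptions.**

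| Mean change in the other 69 (g/dl) | Significant fall | Significant rise |
|---|---|---|
| 0 | about 15% | 0% |
| 0.5 | 0% | about 23% |
| 1.0 | 0% | about 98% |

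With day-0 Hb drawn from mean 12, SD 1.8 and cut at 8 g/dl to mimic the exclusion criterion, the main figures become 14%, 24% and 98%.

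**5. Range of assumptions, without simulation.** Let k patients fall by F and the other 73 − k gain G. The mean change is [(73 − k)G − kF]/73. For k = 4, F = 4, G = 1.0 it is (69 − 16)/73 = +0.73. The paired test gives t = 4.13 (p = 0.0001) if the SD among the gainers is 1.0, and t = 3.35 (p = 0.0013) if it is 1.5. Over k = 3 to 5, F = 3 to 5 and G = 0.5 to 1.5, the mean change is always positive (+0.12 to +1.32):
- G of 1.0 or more: always a significant rise (largest p = 0.019).
- G = 0.5: mostly non-significant (p = 0.014 to 0.60), never a significant fall.

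With F = 4, the mean change reaches zero only when k = 73G/(G + 4), about 8, 15 and 20 patients for G = 0.5, 1.0 and 1.5.

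**6. What a per-patient count would give.** Exact 95% intervals for the proportion with a qualifying fall are 0 to 4.9% for 0 of 73, and 1.5 to 13.4% for 4 of 73. With 88 patients they are 0 to 4.1% for none, and 1.3 to 11.2% for 4. If the true rate is 5%, the chance of at least one case among 73 is 1 − 0.95⁷³ = 98%; if it is 2%, 1 − 0.98⁷³ = 77%.

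**The case against.** A reader might infer that Hb safety is judged only on means, so that large falls leave no trace. The documents do not support that. Median and range are planned, and if they are applied to Hb a low value can surface. Under the assumptions above with day-0 mean 12 and SD 1.8, the lowest Hb is below 8 g/dl in at least about 94% of simulated trials. What stands is narrower: a minimum at a visit does not show whose Hb fell, by how much, or in how many patients.

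A reader might also infer that adverse events can come only from questioning. That too goes too far:
- The adverse-event definition covers signs as well as symptoms.
- Patients are examined at every scheduled visit, and extra Hb tests are allowed when clinically indicated.
- The code list has a free-text entry, and the investigator transfers laboratory values to the same case record form.
- Hb below 5 g/dl leads to hospitalisation, which meets the serious adverse event definition.

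These are real backstops, but none says when a measured fall must be recorded.

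Finally, one might propose simply counting patients below 8 g/dl as adverse events. The protocol's limits conflict, and on the same model such a count performs poorly. It catches 1.3 to 2.0 of the 4 fallers and also flags 1.1 to 3.0 of the other 69, so about 46% to 60% of those flagged had no added fall.

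**Conclusion.** The point holds in a limited form. The named Hb comparisons are all of means, no within-patient fall is summarised, and no rule links a measured fall to an adverse event. With 4 of 73 patients falling an extra 4 g/dl, the paired test detects a fall in about 15% of trials at best. If the other patients recover by 1.0 g/dl, it reports a significant rise in about 98%.

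These percentages rest on assumed Hb inputs. The direction is stable over the ranges examined, but the documents do not show that such falls will occur or how often.

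One feature may add to the problem. If Hb is treated as a secondary outcome, it is analysed per protocol, and patients hospitalised for severe side-effects are withdrawn. The worst falls may then leave the tests. The plan does not say whether Hb is such an outcome, so this is conditional.

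The efficacy conclusion is not affected. This is an inexpensive improvement to what the trial can say on haematological safety.

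**What to change.** Before any threshold is used, reconcile the Hb limits in the Exclusion Criteria, Enrollment and Follow-up, Emergency Care, Annex 1 and Annex 6. Which limits are right is for the investigators to decide.

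Then add to the Statistical Analysis section, for all treated patients with any post-baseline Hb, including those withdrawn:
- each patient's largest Hb fall from day 0, as a distribution and as a listing with baseline Hb;
- the number and percentage crossing fall or low-Hb thresholds that the investigators prespecify, with exact 95% confidence intervals;
- mean Hb by visit, kept as description.

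In the Safety Assessment section, the investigators should state when a measured Hb fall is recorded as an adverse event, whether or not the patient reports a symptom.

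The cost is some wording, one table and one listing from data already collected. Some listed falls will be ordinary variation, which is why baseline Hb belongs beside them, and the reported adverse-event rate may rise.

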## Sample Size Determination and Sampling Technique

### Sample Size Determination

The sample size will be determined according to the WHO (2009) protocol(11); by using the single population proportion formula and calculated assuming 5% margin of error, 95% confidence interval (CI), and treatment failure of 5% and 20% loss to follow-up rate. Accordingly, a minimum of 73 patients will be enrolled.

$$\text{Sample size (n)} = \frac{[(Z \alpha/2)^2 p(1-p)]}{d^2}$$

$$\frac{(1.96)^2 0.05 (1-0.05)}{(0.05)^2} = 73$$

Assuming an additional 20% loss to follow-up rate and withdrawal of consent (15 patients) during the study, at least 88 (73 + 15) patients will be required to bring about a representative sample size.  $n = (1+0.2) 73 = 88$  Where, n= sample size

P=Expected treatment failure (5%)

Z=confidence interval (95%)

d=margin of error (5%)

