### **Operational Definitions and Definition of Terms**

#### **Loss to Follow-Up**

Loss to follow-up occurs when, despite all reasonable efforts, an enrolled patient does not attend the scheduled visits and cannot be found. No treatment outcome will be assigned to these patients. Every effort must be made to schedule a follow-up visit for patients who fail to return to the study site, especially during but also after administration of the study drug. These patients will be classified as lost to follow-up and censored or excluded from the analysis. Patients who are lost to follow-up but who subsequently return to the study site before day 42 will not be turned away and will be encouraged to return for check-up visits. The principal investigator will decide whether the patient is to be classified as lost to follow-up based on his or her history or is to be maintained for the analysis.

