### Laboratory Examination

**Microscopic blood examination:** thick and thin blood smears will be taken from all participants and prepared on the same slide for detection of parasites at all time-points during the 42-day follow-up period. Two smears will be prepared in each case; the first will be stained rapidly with 10% Giemsa for 10–15 min for initial screening and examined by light microscopy immediately. On day 0, in order to rapidly confirm adherence to the lowest parasite density considered for enrollment, initial screening of patients will be made in 10% Giemsa-stained thick film after counting at least 1 parasite for every 6-8 WBCs, which corresponds to approximately 1000 parasites/ $\mu$ l.

The second one will be stained slowly with 3% Giemsa 45–60 min to be examined later by an experienced technician to provide definitive parasite count and speciation. The below formula will be used to determine parasite density.

$$\text{Parasite density (per } \mu\text{l)} = \frac{\text{number of parasites counted} \times (6000-8000)}{\text{Number of leukocytes counted} \approx 200}$$

Two experienced laboratory technicians will examine slides independently. Parasite densities will be calculated from thick blood smears by counting the number of asexual parasites against 200 WBC. If the count is <10 parasites/200 WBC, at least 500 WBC will be counted. A thick blood smear will be declared negative if no parasites are seen in 1000 WBCs and mixed infection has been excluded in 100 fields on thick film. Gametocytes will be detected and counted in thick film. Thin blood smears will be examined to determine parasite species. Gametocytes will be counted in thick blood films against 2000 WBCs.

Two qualified microscopists will read all the slides independently, and parasite densities will be calculated by averaging the two counts. Blood smears with discordant results (differences between the two microscopists in species diagnosis, in parasite density of > 50% or in the presence of parasites) will be re-examined by a third, independent microscopist, and parasite density will be calculated by averaging the two closest counts.

**Hemoglobin:** The hemoglobin concentrations will be measured using a portable spectrophotometer (HemoCue®, Anglom, Sweden), on days 0, 14, 28, and 42.

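### Haemoglobin change is tested by five overlapping paired t-tests limited to patients with both values; one mixed model on all observed Hb is better if drop-out depends on observed Hb

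*Combined protocol and SAP*

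**What the plan says.** Under Laboratory Examination, Hb is measured "on days 0, 14, 28, and 42", and the schedule in Annex 9 agrees. The Statistical Analysis section then plans that a "paired sample t-test will be used to compare mean Hb level between D0 and D14, D0 and D28, D14 and D28", and the list of pairs ends with "D0 and D42, D28 and D42". That makes five of the six possible pairs; only D14-D42 is left out. On error level it says "All comparisons will be performed at 95% CI and significance level of 0.05". No adjustment for the number of tests is stated.

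On who is analysed, the same section says "PP analysis method will be used to analyze secondary outcomes". It does not define the per-protocol set for Hb: it could be one fixed set for all pairs, or a different set for each pair. Of patients lost to follow-up, the Loss to Follow-Up section says "These patients will be classified as lost to follow-up and censored or excluded from the analysis". Sample Size Determination allows for a "20% loss to follow-up rate". The plan has no repeated-measures model for Hb, no rule for missing Hb, and no statement on whether Hb measured after treatment failure or rescue counts.

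**The concern.** A paired t-test discards every patient who lacks one of the two values. Censoring has no meaning in such a test, so for Hb a lost patient is simply excluded from any pair that needs a missing visit. If the patients who leave differ systematically in Hb from those who stay, the mean change among those who stay is not the mean change among those treated.

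The protocol's own rules make this possible. Patients who progress to severe malaria are withdrawn (Patient Discontinuation or Protocol Violation), and Emergency Care lists an Hb below 5 g/dl among the signs of severe malaria. The plan adopts Kaplan-Meier for the primary outcome because follow-up will be incomplete, but has nothing equivalent for Hb.

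The second issue is multiplicity. Five overlapping tests at 0.05 give several chances to declare a change that is not there. What is at stake is the reported Hb recovery after treatment, the only laboratory blood measure on the follow-up schedule apart from the parasite slides and filter-paper spots.

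**Working it through.** **The plan's own figure.** n = 1.96² × 0.05 × 0.95 / 0.05² = 72.99, rounded to 73; 73 × 1.2 = 87.6, rounded to 88. Both reproduce. They concern the failure proportion; nothing is sized for Hb.

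**How much Hb could be missing.** The allowance is 15 of 88 = 17%. If Hb after failure is also dropped, the expected 5% failures add 0.05 × 88 = 4.4, giving 19.4 / 88 = 22%. The simulations below use 20 to 21%.

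**Number of contrasts.** Four visit means allow 4 − 1 = 3 independent differences. Five are tested.

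**Direction of the bias.** Assume equal SD σ at each visit, a common correlation ρ and normal Hb.

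- Loss driven by baseline Hb: the bias in the D0-D42 change is −(1 − ρ) × (baseline mean of completers minus baseline mean of all). If patients with low baseline Hb leave, the bias is downward.
- Loss driven by the D0-D14 change: the slope of the D0-D42 change on it is σ²(1 − ρ) / [2σ²(1 − ρ)] = 0.5. The bias is 0.5 × (excess D14 change among completers). If poor early responders leave, it is upward.
- Random loss: zero.

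**Size.** The documents give no SD, correlation or drop-out strength for Hb, so all of these are assumptions.

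*Setting A:* SD 1.5 to 2.0 g/dl, correlation 0.5 to 0.7, 20% loss by D42, odds of leaving 2.7 to 7.4 times higher per SD lower Hb. Bias in the D0-D42 change, g/dl:

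| Loss driven by | Paired test | Likelihood model, all observed Hb |
|---|---|---|
| Chance | 0.00 | 0.00 |
| Low baseline Hb | −0.09 to −0.27 | 0.00 |
| Low last observed Hb | −0.03 to −0.09 | 0.00 to −0.01 |
| Low unobserved current Hb | +0.03 to +0.11 | +0.08 to +0.24 |

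Hand check of the second row: at SD 2.0 and ρ = 0.5, a bias of −0.27 implies a baseline shift of 0.27 / 0.5 = 0.54. At ρ = 0.7 the formula then gives 0.3 × 0.54 = 0.16; the simulation gave 0.17.

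*Setting B:* true D0-D42 rise 1.0 g/dl, SD 1.8, correlation 0.5 to 0.7, 21% loss. Estimated rise, g/dl:

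| Loss driven by | Paired test | Likelihood model |
|---|---|---|
| Chance | 1.00 | about 1.00 |
| Poor D14 change | 1.13 to 1.20 | about 1.00 |
| Low baseline Hb | 0.71 to 0.90 | about 1.00 |
| Unobserved D42 Hb | 1.10 to 1.28 | 1.15 to 1.31 |

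**At the planned size.** With 88 patients, no true change, SD 1.5 and correlation 0.5, the paired D0-D42 test rejects in about 5% of trials under random loss, 13 to 22% under baseline-driven loss, and 6 to 7% under the other two mechanisms. In the baseline-driven case the bias (−0.14 to −0.20) is about as large as the standard error (0.18).

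**Five tests together.** If Hb does not change at any visit, simulation gives at least one result below 0.05 in 18.0 to 18.9% of trials. Independent tests would give 1 − 0.95⁵ = 22.6%; the five share data, so that figure is too high here.

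**A fixed completer set is no cure.** If the per-protocol set is everyone with a D42 value, baseline-driven loss biases D0-D14 by as much as D0-D42. Conversely, not every pair is affected: under that mechanism with equal correlations, D14-D28 and D28-D42 were unbiased.

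**The case against.** The strongest case against has four parts.

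*The direction is unknown.* A reader might infer that patients who recover poorly leave, so the reported rise is too favourable, by 13 to 20% in Setting B. The documents do not support this. It follows from one assumed mechanism; loss after low baseline Hb gives the opposite sign, and random loss gives no bias. The protocol also works against loss of sick patients: absentees are followed up at home, travel is paid, and anyone ill is asked to return on any day. Many withdrawal reasons, such as consent, vomiting or self-medication, have no evident link to Hb. This part stands: only the possibility of bias is established.

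*The model is not a complete remedy.* A reader might infer that a mixed model removes the problem. It does so only if loss depends on observed Hb. With loss driven by unobserved Hb it was somewhat worse than the paired tests. This stands and has to be handled by a sensitivity analysis.

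*The model's form matters.* A random intercept alone assumes equal correlation between all visits. When correlation decayed with time and loss followed baseline Hb, it gave 0.91 for a true 1.0, against 1.00 to 1.01 with an unstructured covariance. This too stands.

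*Hb is minor.* The safety sections define safety by adverse events and do not name Hb as an endpoint, and no decision depends on an Hb test. True, but the plan commits to five Hb tests, and their results will be read as evidence of recovery.

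**Conclusion.** The point holds in a limited form. The plan tests Hb with five overlapping paired comparisons, each restricted to patients with both values, and has no rule for missing Hb or multiple tests. With the planned loss, the estimated change is biased if drop-out depends on Hb already observed: by 0.03 to 0.27 g/dl in Setting A, and up to 0.29 g/dl (1.00 − 0.71) in Setting B. The sign depends on why patients leave. These sizes rest wholly on assumed SD, correlation and drop-out strength. The false-positive chance of about 18 to 19% across the five tests applies if Hb does not change at any visit.

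That each pair will describe a different group of patients is an inference, since the per-protocol set for Hb is undefined; a single fixed set would not remove the bias. The better analysis is available at little cost, so the change is worth making, but it is an improvement to a non-primary analysis. The cure-rate estimate is unaffected.

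**What to change.** Replace the five paired t-tests with one likelihood-based linear mixed model for Hb:

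- visit (D0, D14, D28, D42) as a factor, with unstructured within-patient covariance (4 × 5 / 2 = 10 parameters, feasible with 88 patients);
- every observed Hb value from all treated patients, including those later lost or withdrawn. Fitted only to patients with complete Hb, the model would give the same mean changes as the paired tests;
- a stated rule on whether Hb after treatment failure or rescue is included;
- one overall test of visit at 0.05, then the D14, D28 and D42 changes from D0 with 95% CIs. If separate p-values are wanted, adjust them; a single model does not do this by itself.

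Add one sensitivity analysis for loss that depends on unobserved Hb: assume the missing D42 values lie below the model's prediction by a range of amounts d. The D42 change then falls by (fraction missing) × d; with 20% missing and d = 1 g/dl, that is 0.20 g/dl. Report the d at which the conclusion would change.

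The cost is revised wording and one procedure in the statistical software already named. No visits, samples or patients are added. Under random loss in the 88-patient simulation the standard error was 0.18 for both methods. The downside is reliance on missing-at-random, which the sensitivity analysis examines but cannot remove.
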